#### Other analyses

To examine feasibility and acceptability we will 1) Track measures of engagement and participation by recording: a) actual recruitment as compared to recruitment goals, to determine the pace at which subjects consent to participate; b) rates of engagement and attendance at intervention sessions, and the number of reminder and other outreach contacts required to keep participants engaged. This will tell us how much staff time is required to get participants to remain involved; c) Track VA clinic service and medication use with the CSUTF and the SUF after post and follow-up assessments by conducting chart reviews. 2) Track costs, including: a) Training of research therapists in the intervention; b) Payments for session attendance. Attendance at training sessions and information on training session duration will be recorded by project staff. We will determine inter-rater reliability for the adherence and competence scales, then calculate mean adherence ratings for intervention congruent and noncongruent behaviors and mean competence ratings. 3) Review supervision notes and interventionist logs to identify content for implementation materials via discussion among the investigators. We will examine CRIS-CAT responses and explore reliability/validity in a schizophrenia sample.

#### Sample Size Considerations

We have powered this RCT for primary hypotheses 1 and 2 of Specific Aim 2 (two outcome measures). We consider the tests for the FU assessment as secondary. A medium effect size at PT (e.g. Cohen's  $d$  = .50) would generally represent a minimum clinically important difference. For example, for the primary outcome in H1, the CAINS Affective-Motivational Deficit Subscale (average rating range: 0–4), we know that  $d$ =.50 represents a .36 point difference in means between EnCoRE and control at PT which is slightly more than 1/3 of the distance

between anchor points (0=No impairment, 1=Mild deficit, 2=Moderate deficit, 3=Moderately Severe deficit, 4=Severe deficit). Because we are testing 2 hypotheses under Specific Aim 2, we specified the alpha level=.05/2=.025 for the sample size calculation. Power was set =.80. We expect 15% attrition at PT. For these specifications and under the primary analysis model, we would need a sample size of N=92 when the correlation between baseline and post-treatment outcome measure = .70. Although, setting this correlation to .70 is reasonable, this correlation could plausibly be lower, requiring the sample size to be greater. Therefore, we reset this correlation to be .63, and found that a sample size of N = 108 would then be required. Calculations were performed assuming a repeated measures design using the Sampsi command in Stata version 8.

## **5.7 Withdrawal of Subjects**

Schizophrenia participants may be removed from the study if the investigator decides that the study is no longer in their best interest, or if a participant fails to follow instructions of the research staff. There are no consequences of a subject's decision to withdraw from the research and the procedures in this study. Participants are free to withdraw at any time, and participation is entirely voluntary.

## **6 Reporting**

All Unanticipated Problems, Serious Adverse Events, Deviations related to this study will be reported to the engaged participating sites within 5 business days of study staff becoming aware of the event. Adverse events that do not meet the criteria for reporting within 5 business days will be reported to the VA Central IRB and the participating sites at the time of continuing review in summary format.

## **7 Privacy and Confidentiality**

All research appointments will be conducted in private rooms with closed doors within the VA Maryland Health Care System (VAMHCS) or the DC VAMC. All participants will receive research information in a private room with the door closed within the VA Maryland Health Care System (VAMHCS) or the DC VAMC. All qualitative interviews and assessments will be conducted in private rooms within the VAMHCS or the DC VAMC. If a Veteran is unable to complete the qualitative interview or study assessment at a VAMC then we will offer to conduct the interview over the phone and strongly encourage the Veteran to choose a confidential location for the interview. All digitally recorded sessions will take place within a room with the door closed at all study locations. If a provider is unable to complete the interview in a private VAMHCS or DC VAMC room then they will be asked to answer the qualitative questionnaire over email. Although no questions should elicit answers with PHI, we will require that providers encrypt all emails as a safeguard.

Digital audio recordings will be saved on a secure VA network, and digital audio files of Veteran and provider qualitative interviews will be posted on a secure website that a VA-approved transcription agency has access to. The transcription agency has completed all training and other requirements to be a contractor with the VA and our research center. Once

the agency has transcribed an interview, the word file of the transcript will be posted on the site, which we will download and store on a secure VA network. The transcription company will not keep a copy of the audio recordings, and will delete the audio recording once the transcription process is complete. The study team will keep a copy of all audio recordings either in electronic or CD form, as required by the VA Records control schedule. Provider qualitative email responses will be stored and analyzed as transcriptions.

Data collected at the DCVA will be mailed back or transported in a locked bag by study staff to the Baltimore VA for data entry and storage. The DCVA utilizes United Parcel Services of America (UPS) for shipping of packages. If data is mailed back, UPS sends an email to the study coordinator ([name]) once it has been shipped and then once it has been received at the Baltimore VA, as a way to track the location of the package. The data being shipped or transported from the DCVA may include paper data containing participant random ID numbers, as well as video or audio recordings of assessments, groups, and individual sessions (only labeled with ID numbers).

Data from the Perry Point VA will be transported back to the Baltimore VA for data entry and storage. This data will be transported in a locked bag by study staff. The data being transported back from the Perry Point VA may include paper data containing participant random ID numbers, as well as video or audio recordings of assessments, groups, and individual sessions (only labeled with ID numbers).

All hard copies of coded research assessment forms will be stored in a locked cabinet in a locked office in the VA Maryland Health Care System, MIRECC Offices ([name]. Consent forms which contain participants' names but not their project ID number are kept in a separate locked cabinet in a locked office at the VA Maryland Health Care System, MIRECC Offices ([name]. The file that links participant names to their project ID number will be stored behind the VA Firewall at all times. Access to the link file will be limited to only study staff listed on this protocol.

Coded electronic data collected in this study will be stored and managed at the VA Maryland Health Care System, MIRECC Offices ([name]), and stored behind the VA firewall. All data, including the investigator's research records and any participant identifiers will be retained in accordance with the Dept. of Veterans Affairs Records Control Schedule (RCS 10-1), and will not be destroyed.

## **8 Communication Plan**

The coordinator of this study is very familiar with the approvals required prior to initiating study activities at each site. They will ensure that all CIRB approvals as well as local IRB and R&D offices have approved the study prior to study implementation. All amendments and modifications for this study will be sent to the engaged participating sites (VAMHCS and DCVA R&D offices). If approval from these participating sites is required prior to implementation, this study will follow those procedures in place.

All study staff will be emailed and briefed during study team meetings on any changes to the protocol and will be provided a copy of the current version of the informed consent form from the coordinator as soon as it is made available. We will have weekly study team meetings and ongoing supervisions to ensure protocol compliance by study staff. Study staff will also be informed on a regular basis to report any non-compliance immediately to the study coordinator and PI of this study. Any incidents of non-compliance will be reported in accordance with VHA Handbook 1058.01 and the VA Central IRB Table of Reporting Requirements. In the event of any serious adverse events, unanticipated problems, or interim results that may impact the conduct of the study, all study sites will be informed immediately via email or study team meeting. The PI of this study will meet with the local facility director and LSI at each site to inform them that the study will no longer require engagement of the local facility.

Document Type: Statistical Analysis Plan

Document Date: April 6, 2021

Outcomes Table

Type of Outcome	Description of Measure	Scale or Score	Time period
Primary	Clinical Assessment Interview for Negative Symptoms (CAINS, Kring et al., 2013), a 13-item measure of negative symptoms that includes two subscales: expression (4 items) and motivation and pleasure (9 items).	CAINS Motivation and Pleasure Scale (CAINS-MAP)	Baseline-12 weeks
Primary	Clinical Assessment Interview for Negative Symptoms (CAINS, Kring et al., 2013), a 13-item measure of negative symptoms that includes two subscales: expression (4 items) and motivation and pleasure (9 items).	CAINS Motivation and Pleasure Scale (CAINS-MAP)	Baseline-24 weeks
Primary	Social Functioning Scale (SFS, Birchwood et al., 1990) measures engagement in social activities through assessment of seven domains: Social Engagement/Withdrawal, Interpersonal Communication, Prosocial, Independence-Performance, Recreation, Independence-Competence, and Employment. In the present analysis, we used a total score for the SFS including all subscales except the employment subscale.	Social Functioning Scale	Baseline-12 weeks
Primary	Social Functioning Scale (SFS, Birchwood et al., 1990) measures engagement in social activities through assessment of seven domains: Social Engagement/Withdrawal, Interpersonal Communication, Prosocial, Independence-Performance, Recreation, Independence-Competence, and Employment. In the present analysis, we used a total score for the SFS including all subscales except the employment subscale.	Social Functioning Scale	Baseline-24 weeks
Secondary	Clinical Assessment Interview for Negative Symptoms (CAINS, Kring et al., 2013), a 13-item measure of negative symptoms that includes two subscales: expression (4 items) and motivation and pleasure (9 items).	CAINS Social Motivation and Pleasure Scale (CAINS-MAP)	Baseline-12 weeks
Secondary	The Role Functioning Scale (RFS, Goodman et al., 1993) is a reliable and valid interview that assesses four domains: Working Productivity, Independent Living/Self Care, Family Network Relationships, and Immediate Social Network Relationships (e.g., Edmondson et al., 2012, Yamada et al., 2010). In the present analysis, we summed ratings of Independent Living/Self Care, Family Network Relationships, and Immediate Social Network Relationships as our measure of role functioning. We excluded Working Productivity because our sample was comprised largely of adults who were retired or not working.	Role Functioning Scale	Baseline-12 weeks
Secondary	Brief University of California San Diego Performance-based Skills Assessment (UPSA; Mausbach et al., 2007) assesses the respondent's capacity to perform tasks similar to those encountered in daily life in two domains: 1) financial skills, in which participants are required to count change, make change from an item purchased at a store, and write a check for a utility bill, and 2) communication skills, in which participants are asked to demonstrate how to use a telephone to dial emergency services, call information to ask for a telephone number, and call a physician to reschedule a medical appointment. For each domain, the total percent correct is calculated and converted to a standardized score ranging from 0 to 50. A summary score is then calculated by summing the two domain scores (range = 0–100), with higher scores indicating better functional capacity.	UPSA-B Total Score	Baseline-12 weeks
Secondary	The 25-item Maryland Assessment of Recovery Survey (MARS; Drapalski et al., 2012) assesses personal recovery in serious mental illness with items addressing having control over one's life, strength to meet and solve challenges, and belief in one's abilities (e.g., "I have abilities that can help me reach my goals", "I am able to set my own goals in life", "I can influence important issues in my life").	MARS Total Score	Baseline-12 weeks

Secondary	Clinical Assessment Interview for Negative Symptoms (CAINS, Kring et al., 2013), a 13-item measure of negative symptoms that includes two subscales: expression (4 items) and motivation and pleasure (9 items).	CAINS Social Motivation and Pleasure Scale (CAINS-MAP)	Baseline-24 weeks
Secondary	The Role Functioning Scale (RFS, Goodman et al., 1993) is a reliable and valid interview that assesses four domains: Working Productivity, Independent Living/Self Care, Family Network Relationships, and Immediate Social Network Relationships (e.g., Edmondson et al., 2012, Yamada et al., 2010). In the present analysis, we summed ratings of Independent Living/Self Care, Family Network Relationships, and Immediate Social Network Relationships as our measure of role functioning. We excluded Working Productivity because our sample was comprised largely of adults who were retired or not working.	Role Functioning Scale	Baseline-24 weeks
Secondary	Brief University of California San Diego Performance-based Skills Assessment (UPSA; Mausbach et al., 2007) assesses the respondent's capacity to perform tasks similar to those encountered in daily life in two domains: 1) financial skills, in which participants are required to count change, make change from an item purchased at a store, and write a check for a utility bill, and 2) communication skills, in which participants are asked to demonstrate how to use a telephone to dial emergency services, call information to ask for a telephone number, and call a physician to reschedule a medical appointment. For each domain, the total percent correct is calculated and converted to a standardized score ranging from 0 to 50. A summary score is then calculated by summing the two domain scores (range = 0–100), with higher scores indicating better functional capacity.	UPSA-B Total Score	Baseline-24 weeks
Secondary	The 25-item Maryland Assessment of Recovery Survey (MARS; Drapalski et al., 2012) assesses personal recovery in serious mental illness with items addressing having control over one's life, strength to meet and solve challenges, and belief in one's abilities (e.g., "I have abilities that can help me reach my goals", "I am able to set my own goals in life", "I can influence important issues in my life").	MARS Total Score	Baseline-24 weeks

Statistical Analysis Plan

Statistical Analysis Overview: Proposed sample size of N = 108 was chosen to detect a standardized mean difference in change from baseline to post-treatment equal to 0.50 between the intervention and active control arms. There were two primary outcome scales – one measuring social functioning and the other measuring negative symptoms. Threshold for statistical significance was $p < 0.05$ with no adjustment for multiple comparisons.

Statistical Test of Hypothesis: The analysis of the primary outcomes utilized a mixed effects model accounting for a random therapy group effects and the analysis included all available data at baseline, post-treatment, and follow-up time-points. Error terms across time points were assumed correlated with unstructured correlation matrix. To test time-specific hypotheses, terms in the mean model included separate indicators for post-treatment and follow-up time points, and interaction terms between these indicators and condition. Based on randomization to treatment condition, the model assumed no differences at baseline, i.e. any differences were assumed to be due to random sampling error. All continuous outcome scales were checked for skew, and an appropriate transformation was applied as needed. Statistical significance was defined as $p \leq .05$. All analyses were performed using SAS version 9.4. In moderator analyses we examined whether treatment effects on the primary outcomes (CAINS MAP, SFS) differed according to baseline dysfunctional attitudes measured by the DAS and SARA-Q. We also examined whether baseline negative symptoms (CAINS MAP) modified treatment effects for the SFS. Each moderator variable was dichotomized at the median. In separate models, the moderator and interaction terms with the moderator were added to the primary linear mixed effects models to test whether treatment effects at post-treatment and follow-up time points differed for those above versus below the median.

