## 3.0 Objectives

The goal of this study is to evaluate an innovative psychosocial intervention package that will incorporate evidence-based treatment strategies to target the affective-motivational

deficits, negative expectancies, and behavioral skills deficits that are central to the maintenance of negative symptoms. The intervention - called EnCoRE (Engaging in Community Roles and Experiences) - will include strategies aimed at teaching Veterans with schizophrenia and negative symptoms ways to (1) overcome deficits in anticipatory pleasure, (2) increase intrinsic motivation for goal-directed activities, (3) reduce expectancies for failure, and (4) perform skillfully in new social situations, all of which can impact implementation of new skills and behaviors. Rather than develop a new set of intervention strategies, we will include within EnCoRE evidence-based strategies for these treatment domains. In addition, we will collect qualitative information both from Veterans concerning their perceptions of the strengths, weaknesses, and barriers to participation in EnCoRE, as well as from a sample of mental health providers who work with Veterans with schizophrenia and negative symptoms, in order to inform a larger scale implementation trial should EnCoRE prove effective here.

Following a short pilot to train interventionists and refine the manual, we will conduct a randomized controlled trial to test the efficacy of EnCoRE in improving ratings of negative symptoms, functional outcomes, and engagement in community activities in a sample of Veterans with schizophrenia and negative symptoms (n=108). Participants will be randomized either to EnCoRE or a health-related control group. These goals fit well within the objectives of the RR&D program of funding research aimed at studying rehabilitation interventions focused on maximizing functional recovery and assisting in the integration of Veterans into civilian life. Specifically, we will address the following Specific Aims:

Specific Aim 1: Train therapists and refine the EnCoRE manual in a preliminary trial with 10 Veterans with schizophrenia and negative symptoms.

Specific Aim 2: Conduct a randomized controlled trial (n=108, medium effect, alpha=.05) to test the efficacy of EnCoRE in producing positive changes at post-treatment and 3-month follow-up on the primary outcomes of negative symptoms and social and community functioning.

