### Hypotheses

Hypothesis 1 (H1): Veterans exposed to EnCoRE will have lower mean scores than those in the control condition on the affective-motivational deficit subscale of the CAINS at post-treatment. The EnCoRE group will continue to have a lower mean than the control group at FU (secondary hypothesis). . Letting Y1, Y2, and Y3 be values for the motivational deficit subscale of the CAINS at BL, PT, and FU respectively, and Tx condition the treatment indicator (Tx condition=1, if EnCoRE; Tx=0 if control condition), the analysis model for Hypothesis 1 (post-treatment) will be:  $Y_2 = Y_1 + \text{Site (or Group)} + \text{Tx condition} + \text{error}$  (ANCOVA). Substantively relevant BL covariates found to significantly differ between treatment conditions, even after randomization, would be added. We will also check if there is a covariate by treatment interaction in this case. Significance test of the Tx condition coefficient will test hypothesis 1. The analysis model for the

comparison at FU will be similar, but will include Y2 and Y3 as repeated responses and include a random effect to account for correlation between the two. Thus, it will be a linear mixed model with adjustment for BL (Y2 and Y3 repeated response and adjustment for Y1). A time and group-by-time interaction term will be added (time indicating FU versus PT) in order to estimate the difference of means at FU assessment. A specified contrast using the mixed model will test the hypothesis that the mean affective-motivational deficit in the EnCoRE condition will continue to be less than in the control condition.

Hypothesis 2 (H2): Veterans exposed to EnCoRE will have a higher mean score than controls at post-treatment on the SFS and RFS. The EnCoRE group will continue to have higher a mean score than control at the 3 month FU. The analysis model for H2 will be parallel to those for H1.

Hypothesis 3 (H3): Veterans exposed to EnCoRE will have higher mean scores than controls at post-treatment and at FU on the UPSA-B total score.

Hypothesis 4 (H4). Veterans exposed to EnCoRE will have higher mean ratings on the MARS than control at PT and FU. Analysis models for H4 will be parallel to those for H1.

Hypothesis 5 (H5): General cognitive ability and symptoms of psychosis will not impact the effectiveness of the intervention for negative symptoms and community functioning at PT and FU (See analysis below for H6).

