Hypothesis 6 (H6): Greater ratings of consumer participation in and satisfaction with the intervention will be associated with better PT and FU outcomes. For each of the potential modifiers in H5 and H6, we will re-fit the primary analysis model for PT outcomes after adding two terms, the potential modifier and the interaction term between the treatment condition indicator (Tx condition) and the potential modifier. The variable will be a modifier if the coefficient for the interaction term is statistically significant (p-value<.05). A similar model will be used to assess modification at FU but there will be additional interaction terms with time (including 3-way interaction time\*treatment condition\*modifier), in order to estimate modifying effects at FU (i.e. separate effects at FU vs. PT).

Hypothesis 7 (H7): Improvements on ratings of attitudes/beliefs (e.g. DBS, FTT score) in the EnCoRE condition from BL to PT and FU will be positively associated with improvements in symptom and functioning outcome measures from BL to PT and FU, respectively. Change scores will be computed for attitudes/beliefs and recovery, and for symptom and functioning scales. Pearson correlations will be calculated and significance tests of the null hypothesis of zero correlation will be conducted. Note: These tests of association can be conducted even if improvement on ratings of self-efficacy and recovery are not significant in H3.

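### The SAP tests CAINS-MAP and SFS at an unadjusted .05 and labels both primary at 12 and 24 weeks, although N=108 was justified at .025 for two post-treatment hypotheses

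*SAP*

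**What the plan says.** **Protocol.** Sample Size Considerations (section 5.6) powers the trial for primary hypotheses 1 and 2, counts two outcome measures, and gives its reason for the split: "Because we are testing 2 hypotheses under Specific Aim 2, we specified the alpha level=.05/2=.025 for the sample size calculation". It adds: "We consider the tests for the FU assessment as secondary". The H1 text, in both Hypotheses and section 5.6, also labels the follow-up comparison a secondary hypothesis.

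Other protocol text is less clear-cut:

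- Specific Aim 2 in section 3.0 carries the bracket "n=108, medium effect, alpha=.05".
- The Aim 2 wording, there and in section 5.6, names both post-treatment and 3-month follow-up for the primary outcomes.
- H2 names two functioning measures, SFS and RFS.

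**SAP.** The Statistical Analysis Overview keeps N=108, tied to a standardized difference of 0.50 at post-treatment. It says "There were two primary outcome scales" and sets p<0.05 "with no adjustment for multiple comparisons". The Outcomes Table gives CAINS-MAP and SFS a primary row at 12 weeks and another marked "Baseline-24 weeks"; RFS appears only as secondary. The Statistical Test of Hypothesis section fits a separate treatment effect at each time point.

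**The concern.** The reason given for .025 is that two hypotheses are tested. That reason applies at analysis as much as at sizing, but the SAP keeps the sample size and drops the split without comment. It also gives the primary label to follow-up comparisons that the protocol's most explicit text calls secondary. It sets no order of testing and does not require both scales to succeed.

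A reader therefore cannot tell which result would count as success. Nothing in the SAP excludes reporting any one of the four primary-labelled comparisons, at nominal p<.05, as a primary finding. At stake is the false-positive rate behind the trial's main claim.

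**Working it through.** **1. Reproduce the sample size.** Inputs from Sample Size Considerations: d=.50, power .80, alpha .025, 15% attrition, baseline to post-treatment correlation .63 (N=108) or .70 (N=92). Sidedness is not stated; two-sided is assumed.

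n per arm = 2(z₁₋α/₂ + z.₈₀)² V / .5², and total = 2n/.85. For ANCOVA, the protocol's primary model, V = 1−ρ². For a change score, V = 2(1−ρ).

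Example: α=.025, ρ=.63 gives 2 × (2.2414+0.8416)² × .6031 / .25 = 45.86 per arm, and 91.72/.85 = 107.9.

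| Variance | α (two-sided) | ρ=.63 | ρ=.70 |
|---|---|---|---|
| ANCOVA | .025 | 107.9 | 91.2 |
| ANCOVA | .05 | 89.1 | 75.3 |
| Change score | .05 | 109.3 | 88.6 |
| Change score | .025 | 132.4 | 107.4 |
| *Protocol states* | *.025* | *108* | *92* |

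With n rounded up per arm, ANCOVA at .025 gives 92/.85 = 108.2 and 78/.85 = 91.8. This is the best match to both stated figures.

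**2. Power at N=108.** Assessed per arm: 108 × .85/2 = 45.9. With ρ=.63, d/SE = .5/√(2×.6031/45.9) = 3.084. Power is Φ(3.084−2.241) = .80 at .025 and Φ(3.084−1.960) = .87 at .05. Both are before any therapy-group clustering.

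**3. Family-wise error, two post-treatment tests.** For independent tests it is 1−(1−α)². The lower ends below come from multivariate normal simulation with a between-scale correlation of .7. The documents give no such correlation, so 0 to .7 is an assumed range.

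| Level per test | Two-sided | In EnCoRE's favour only |
|---|---|---|
| .05 | 8.4-9.8% | 4.2-5.0% |
| .025 | 4.3-5.0% | 2.1-2.5% |

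Check at independence: 1−.95² = 9.75%; 1−.975² = 4.94%.

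**4. Family-wise error if all four primary rows count, at .05 each.** This also needs the correlation between the post-treatment and follow-up tests, which the documents do not give. Two assumptions were tried, each with between-scale correlation 0 to .7:

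- The protocol's .63-.70 holds between every pair of visits. After baseline adjustment this becomes ρ/(1+ρ): .63/1.63 = .39 to .70/1.70 = .41. Error: 15.2-17.9% two-sided, 7.7-9.1% in EnCoRE's favour.
- A correlation of .63-.70 remains after baseline adjustment. Error: 13.6-16.5% two-sided.

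Full independence gives 1−.95⁴ = 18.5%, but that needs uncorrelated visits and is not plausible.

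**The case against.** Five points can be made for the SAP.

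- **The .025 was only a sizing figure.** This stands. No H1 or H2 text gives a decision threshold, Aim 2 carries alpha .05, and the only explicit p-value criterion in the protocol is .05, for the modifier tests. A reader might infer that the SAP broke a prespecified testing level. The documents do not support that; .025 as a testing level is an inference from the stated reason. The Aim 2 figure does, however, fit an overall level that the sizing section then divides.
- **The 24-week primary label is not purely the SAP's invention.** This stands in part. The Aim 2 wording names follow-up on the primary outcomes. The H1 text and the sizing section are more explicit, and both rank follow-up as secondary.
- **The table may only be listing visits.** This is possible, since the Overview counts two scales and ties N to post-treatment. Step 4 then does not apply, but step 3 does.
- **A change-score formula at .05 nearly gives the same N.** It gives 109.3 and 88.6, and the SAP does speak of a difference in change. It fits the stated 92 less well and goes against the protocol's own account, which names .025 and the primary analysis model.
- **The lack of adjustment is disclosed.** It is. What is missing is a reason and any link to the sizing section. A reader might also infer that the change was undocumented or made after results were seen. Only the supplied text can be judged, and it does not say.

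**Conclusion.** The mismatch is real and unreconciled. N=108 rests on .025 for each of two post-treatment hypotheses, while the SAP tests at .05 unadjusted and extends the primary label to 24 weeks. On the narrower reading of its table, family-wise error is 8.4-9.8% instead of 4.3-5.0%, about double; for errors favouring EnCoRE it is 4.2-5.0% instead of 2.1-2.5%. The 14-18% figure holds only if all four rows count as primary and rests on assumed correlations, so it should not be quoted as the established error rate.

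The sample size itself is not at fault: it gives the planned .80 power at .025. The textual conflict is certain; a breached testing rule is not shown.

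The status of RFS is a related inconsistency that starts in the protocol, where H2 names two functioning measures but the sizing section counts two outcome measures in all. The SAP's two scales match that count, but the SAP does not say why SFS was kept as primary and RFS was not.

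**What to change.** The SAP is in the past tense and already describes the sample, so its text should be left standing. Add a dated, documented note that:

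1. Takes CAINS-MAP and SFS at post-treatment as the primary family, matching the two outcome measures in the protocol's sizing section. Report both tests judged at two-sided .025 each, or by Holm at .05 overall, beside the unadjusted p-values. State which method is used, and base the primary conclusion on the adjusted result.
2. Reports the 24-week comparisons as secondary, following the sizing section, and acknowledges that the Aim 2 wording mentions follow-up.
3. Discloses that H2 named both SFS and RFS, that the sizing section counts two outcome measures, and that the SAP made RFS secondary. Any Holm result over CAINS-MAP, SFS and RFS is a sensitivity display only, so that there is one primary family.

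**Cost.** One note and a few adjusted p-values; no new data. Before therapy-group clustering, power per test is .80 at .025, as planned, instead of .87 at .05. Holm on the two tests gives .80 if only one scale improves by d=.50 and .84-.86 if both do.
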